1. RATIONALE

Statement of Problem: Obesity is an epidemic, a major public health concern, and is a significant risk factor for progression and mortality from prostate cancer. Research from our group and others suggest that weight loss interventions consisting of exercise and reduction in dietary fat may play an important role in the prevention of prostate cancer progression (secondary prevention).

Objectives: In this project we seek to establish the potential efficacy of weight loss for preventing the progression of prostate cancer by evaluating the effect of a 4-9-week weight loss intervention on the proliferation and apoptosis of prostate cancer tissue from radical prostatectomy specimens. We also seek to validate intermediate serum biomarkers that reflect or influence the weight loss-induced changes in prostate cancer tissue and which can be applied in future large-scale intervention studies aimed at secondary prostate cancer prevention in prostate cancer survivors.

Based on the background and preliminary data presented in this proposal **we hypothesize** that:

- (1) Overweight and obese men that lose weight over a 4-9-week period prior to radical prostatectomy will have decreased proliferation and increased apoptosis of prostate cancer tissue relative to men that do not achieve weight loss, and that prostate cancer tissue obtained from men with weight loss will show evidence of a decreased tone of the local IGF axis including reduced phosphorylation of the IGF1 receptor, as well as lower levels of IGF-1 protein levels relative to men that do not lose weight.
- (2) Serum from men that lose weight will decrease the proliferation and increase the apoptosis of LNCaP cells in ex-vivo bioassays to a greater degree than serum obtained from men that do not lose weight, and that serum IGF-I levels will also fall with weight loss while IGFBP-1 levels will rise.
- (3) The weight loss-induced changes in serum ex-vivo bioassay results and serum IGF-1 & IGFBP-1 levels will directly correlate with the proliferative, apoptotic, and IGF axis changes seen in prostate cancer tissue. Specifically, we expect that: (a) Increased weight loss will correlate with a fall in serum IGF-I and a rise in serum IGFBP-1 as well as with a reduction in the ex-vivo proliferation bioassay and increase in ex-vivo apoptosis bioassay. (b) Increased weight loss will correlate with increased apoptosis staining and decreased Ki67 staining in the prostate cancer tissue. (c) The post-intervention change in the serum ex-vivo proliferation and apoptosis bioassays and serum IGF-I and IGFBP-1 levels will directly

correlate with the change in tissue proliferation and apoptosis making these markers clinical tools for secondary prevention prostate cancer weight loss trials.

Objective 1. To evaluate if weight loss prior to radical prostatectomy in overweight and obese men results in antiproliferative and pro-apoptotic effects on prostate cancer tissue histopathology. Overweight and obese men that have elected to undergo radical prostatectomy will be randomized to a control group (no weight loss) vs. a 4-9-week weight loss program followed by radical prostatectomy. Proliferation (Ki67) and apoptosis (TUNEL) of the prostate cancer tissue will be compared between the groups. We will also compare the proliferation and apoptosis indices between the baseline prostate needle biopsy specimens and corresponding radical prostatectomy specimens. In addition, prostate cancer tissue IGF-axis RNA and protein levels (IGF-1, total and phospho-IGF-1 receptor, and down-stream molecules), will be compared between the weight loss and control groups.

Objective 2. To evaluate if weight loss prior to radical prostatectomy in overweight and obese men impacts on the circulating levels of IGF-related analytes and on the Ex-vivo mitogenic and apoptotic activity of patient sera on LNCaP cell lines. The ex-vivo mitogenic and apoptosis bioassay in LNCaP cells will be performed on pre and post sera from the Control Group – No Weight Loss and Weight Loss Group at baseline and prior to radical prostatectomy. In addition we will compare baseline and post-intervention serum IGF-I and IGFBP-1 levels by ELISA.

Objective 3. To determine if the weight loss-induced changes in the serum biomarkers/bioassays from Objective 2 correlate with prostate tissue histo-marker changes in Objective 1. This analysis will assess if these serum biomarkers can therefore be used as surrogate biomarkers for future large-scale secondary prevention trials in overweight and obese prostate cancer survivors to monitor the success of weight loss intervention. For example, if the degree of LNCaP apoptosis in the ex-vivo apoptosis bioassay correlates with apoptosis in prostate cancer tissue, then the ex-vivo apoptosis bioassay may serve as a useful intermediate bioassay in large-scale trials to monitor the potential efficacy of weight loss in delaying prostate cancer progression or similarly, IGF-I or IGFBP-1 may prove to be the most predictive circulating indicator of prostate tumor apoptosis.

Long-Term Objectives: Our long term objective is to establish weight loss as an effective treatment to slow prostate cancer progression (secondary prevention) in overweight and obese prostate cancer survivors. If our presently proposed trial is found to be positive, indicating that weight loss results in improvements in the proliferative and apoptotic indices in malignant epithelium, our next trial (**intermediate goal**) will be a large scale, multi-site study evaluating if weight loss impacts on PSA doubling time in men with a rising PSA after primary therapy for prostate cancer. Given that PSA doubling time is becoming established as a surrogate for prostate cancer survival, results from this larger scale trial will determine the need for weight loss strategies in overweight and obese prostate cancer survivors.

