Statistical Design: The statistical design of this study is a randomized repeated measures utilizing random mixed block sizes known only to the statistician constructing the randomization list to assign subjects to two study arms in a ratio of 7:6, weight loss to no weight loss.

Sample Size Determination: An evaluable sample of at least 60 subjects (no weight loss=30, weight loss=30) is expected to provide 80% power to detect an effect size of 0.74 using a two group t-test with a 0.050 two-sided significance when comparing the apoptotic index (primary outcome variable) in the radical prostatectomy malignant epithelium between the weight loss and no Weight Loss Group. The apoptotic index will be measured in the malignant epithelium with the highest Gleason grade. To account for a post-randomization attrition rate of up to 15% in the Weight Loss Group, a total of 35 subjects will be randomized to the Weight Loss Group, thus bringing the total sample size to 65 subjects. Kim et al. observed an effect size of 1.74 on apoptotic index using a nutritional intervention in a similar study.⁶⁴

Data Analysis: Data analyses will be performed on randomized subjects who complete the study. All parameters measured will be summarized descriptively. The number of subjects, mean, standard error of the mean, median and min-max values will be presented for continuous parameters and the number and percentage of subjects in each category will be presented for categorical parameters. No imputation of missing data is planned. Demographic and baseline characteristics will be summarized using descriptive statistics overall and by treatment group to assess baseline comparability. Treatment groups will be compared using the appropriate nonparametric tests for categorical parameters and analysis of variance models for continuous parameters.

Primary Outcome Variable: The primary outcome variable is apoptotic index of the highest Gleason grade malignant epithelium in the radical prostatectomy specimen. The primary objective is to compare the mean apoptotic index between the Weight Loss Group and the Control Group-No Weight Loss. The two independent sample t-test will be used to compare the index between the groups. If the index is non-normally distributed we will use the Wilcoxon rank sum test. Next, linear regression models will be constructed to test whether the treatment effect

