Secondary Statistical Analyses: The statistical methods for these analyses will be analysis of variance (ANOVA), linear regression, and correlation analysis. ANOVA will be used to determine if the serum biomarkers (IGF-I, IGFBP-1, proliferation and apoptosis bioassays) change over the course of time. These models will include a term for time, treatment (weight-loss versus no weight loss) and the time by treatment interaction effect. We will also construct ANOVA models for weight and body fat over time to determine if the treatment by time effect (intervention effect) is significant. Next, linear regression models will be constructed for each biomarker to assess the factors that predict change in that marker. Predictors will include actual weight loss (percent change), group, grade, PSA, percent body fat, and demographic factors. These models will allow us to assess the direct effect of weight loss on each of the serum biomarkers and allow for the assessment of whether weight change or intervention is the primary factor predicting change in the biomarkers. This assessment is required due to the fact that the intervention will have varying effects on weight based on the amount of subject compliance with the weight loss regime. Regression models will also be constructed to compare the groups with respect to the pre-prostatectomy biomarkers and the tissue markers and the between group tissue markers (apoptosis, Ki67 staining). A separate model will be constructed for each marker including the predictors of group, grade, PSA, percent body fat and demographic factors. Next, we will construct regression models to determine if the biomarkers, or change in biomarkers, affect the post-op pathology. Ordinal regression will be used for post-op pathology. These models will include terms for the demographic factors and for each of the biomarkers. Since there are a large number of biomarkers we will first construct single biomarker models which will include the covariates for each outcome and then combine together all significant markers into multiple regression models. Finally, we will use the Spearman correlation to test for correlations between pre-prostatectomy biomarkers and the tissue markers. This analysis will specifically address **Objective 3** of the proposal, that being to determine if a correlation exists between serum biomarkers and tissue biomarkers. The Spearman correlation is a non-parametric rank based correlation measure that does not depend on the assumption that the markers are normally distributed.

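### Objective 3 treats a serum-tissue correlation as validating a surrogate, but its only dedicated analysis is at least eight uncorrected Spearman tests of whether rho differs from zero

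*Combined protocol and SAP*

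**What the plan says.** The aim is stated strongly in section 1 (Rationale). The Objectives paragraph says "We also seek to validate intermediate serum biomarkers". Hypothesis 3(c) says that correlation with the tissue changes would make the serum measures clinical tools. Objective 3 says the analysis will assess whether they can be used as surrogates in later large trials. It gives the apoptosis bioassay as an example (if it correlates with tissue apoptosis, "then the ex-vivo apoptosis bioassay may serve as a useful intermediate bioassay in large-scale trials") and adds that "IGF-I or IGFBP-1 may prove to be the most predictive circulating indicator of prostate tumor apoptosis".

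The analysis is much narrower. In section 3, under Secondary Statistical Analyses, the Spearman paragraph is the one said to address Objective 3 specifically, and its purpose is "to determine if a correlation exists between serum biomarkers and tissue biomarkers". The same section names four serum markers (IGF-I, IGFBP-1 and the two ex-vivo bioassays) and two tissue markers (apoptosis and Ki67). For these correlations the plan gives no significance level, minimum coefficient, confidence-interval requirement, lead pair, multiplicity adjustment or validation step.

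Sample Size Determination covers the primary comparison only: "80% power to detect an effect size of 0.74" with 30 evaluable men per arm, "using a two group t-test with a 0.050 two-sided significance".

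**The concern.** The conclusion the plan wants and the test it specifies do not match. Rejecting rho = 0 shows that two measurements are associated across men. It does not show that a serum change produced by weight loss stands in for a tissue change produced by weight loss, which is what a surrogate claim needs. A weak association can pass such a test, and with at least eight pairs and no adjustment, one may pass by chance.

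What is at stake is the interpretation of Objective 3. If the plan is followed as written, a weak or chance correlation could be reported as validating a serum marker for monitoring weight-loss interventions in later trials.

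**Working it through.** **Inputs.** From the plan: 30 + 30 = 60 evaluable men; completers only, no imputation; four serum and two tissue markers. Assumed, because the plan is silent: the two-sided 0.05 level of the primary test carries over to the correlations, and both arms are pooled.

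**The plan's own figure.** Noncentral-t power for 30 per arm, d = 0.74 and two-sided 0.05 is 80.5%, so the stated 80% reproduces. No corresponding figure is given for Objective 3.

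**Smallest significant correlation.** The critical value is r = t / sqrt(n − 2 + t²), with t the 0.975 quantile on n − 2 degrees of freedom. For n = 60, t(58) = 2.002, so r = 2.002 / sqrt(58 + 4.007) = 0.254 and r² = 0.065. Simulating the null distribution of Spearman's rho at n = 60 (200,000 permutations) gives 0.255. For Spearman, 6.5% is a share of the variance of ranks.

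| n | critical value | squared |
|---|---|---|
| 65 | 0.244 | 6.0% |
| 60 | 0.254 | 6.5% |
| 50 | 0.279 | 7.8% |
| 40 | 0.312 | 9.7% |

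**Precision at that limit.** By Fisher's z, atanh(0.254) = 0.260 and the standard error is 1/sqrt(57) = 0.1325. The interval on the z scale is 0.260 ± 0.260, which back-transforms to about 0.00 to 0.48.

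**Number of tests.** 4 × 2 = 8 pairs. Hypothesis 3 also mentions tissue IGF-axis changes, so eight is a floor.

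**Chance of at least one significant result with no true association.**
- Independent tests: 1 − 0.95⁸ = 33.7%.
- Correlated markers, by simulating a 4 × 2 Spearman grid at n = 60: 32%, 28% and 21% for assumed serum/tissue inter-marker correlations of 0.3/0.3, 0.5/0.5 and 0.8/0.5.
- Counting only results in the predicted direction, independent tests: 1 − 0.975⁸ = 18%.

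**Predicted directions.** Hypothesis 3(a)-(b) expects weight loss to lower IGF-I, the proliferation bioassay and Ki67, and to raise IGFBP-1, the apoptosis bioassay and apoptosis staining. The implied signs are:

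| Serum marker | Ki67 | Apoptosis (TUNEL) |
|---|---|---|
| IGF-I | + | − |
| IGFBP-1 | − | + |
| Proliferation bioassay | + | − |
| Apoptosis bioassay | − | + |

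Four of the eight are inverse, so the statement that the markers will directly correlate cannot be taken literally for all pairs.

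**Effect of adjustment.** Holm over eight starts at 0.05/8 = 0.00625. At n = 60 the critical value becomes 0.349 (12.2% of rank variance). At a true correlation of 0.40, atanh(0.40) × sqrt(57) = 3.20. Normal-approximation power is then Φ(3.20 − 1.96) = 89% unadjusted and Φ(3.20 − 2.73) = 68% at that first step.

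**The case against.** The best defence is that Objective 3 is a secondary analysis in a small mechanistic trial with one prespecified primary outcome, where uncorrected correlations are common. Objective 3 is also hedged: it offers an example and says what a marker may do. Nor is the analysis unusually insensitive. The primary effect size of 0.74 converts to r = 0.74 / sqrt(0.74² + 4) = 0.35, which is also roughly the true correlation detectable with 80% power at n = 60. All of this stands, and it would be a full answer if the plan called the correlations exploratory. It does not. The Objectives paragraph and hypothesis 3(c) claim validation and clinical tools without a hedge.

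The single-marker screen in Secondary Statistical Analyses is no answer either. It belongs to the regression models, and carrying forward the significant markers is selection, not error control.

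Four stronger readings are tempting, but the documents do not support them:
- **The plan adopts a rule that any significant correlation validates a marker.** No such rule is written. It is inferred from the absence of any other criterion, as is the 0.05 level.
- **There is no expected sign, so a wrong-direction result would count as success.** Hypothesis 3(a)-(b) gives a direction for every marker. The defect is the loose wording about direct correlation and the absence of signs from the analysis text.
- **A false marker would become the endpoint of the next large trial.** Objective 3 gives the serum markers a monitoring role. The Long-Term Objectives and the Significance paragraph make PSA doubling time the next trial's endpoint and make that trial depend on the tissue result.
- **The false-positive rate is 34%.** That is the value under independence. Section 2 attributes the bioassay effects to the IGF-axis changes, so the serum markers are probably correlated and the rate lower.

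**Conclusion.** The point holds: the plan is wrong as written, because the stated test cannot support the stated conclusion. A Spearman test of rho = 0 may identify an association. It cannot validate a serum marker as a surrogate or clinical tool.

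The threshold of 0.254 assumes two-sided 0.05, 60 complete pairs and pooled arms; fewer complete pairs would raise it. The 21-34% range is for eight null tests. Its lower end rests on assumed inter-marker correlations, since the plan reports none. The 18% figure adds the restriction to predicted signs and assumes independence. The primary analysis is not affected.

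**What to change.** 1. In the Rationale, replace the language of validation and surrogacy with *candidate marker for further study*, and align hypothesis 3(c) with it.
2. State in Objective 3 and in Secondary Statistical Analyses that a significant correlation is not evidence of surrogacy.
3. List all eight serum-tissue pairs with the signs in the table above, in place of the wording about direct correlation. The list should also say whether each measure is a change or a level, because Objective 3 speaks of changes and the Spearman paragraph of pre-prostatectomy markers.
4. Report every coefficient with its 95% confidence interval, whether significant or not.
5. Either label the whole set exploratory, or base any claim of association on Holm-adjusted p-values across the eight pairs. Keep IGF-I and IGFBP-1 on the same footing as the bioassays, since section 2 names the IGF axis as the focus of the proposal.

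The cost is wording and a little analysis, with no extra patients, visits or assays. The downside is a weaker claim. If Holm is chosen, the first-step threshold rises from about 0.25 to about 0.35, and first-step power at a true correlation of 0.40 falls from about 89% to about 68%.

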2. BACKGROUND AND SIGNIFICANCE

Introduction: Obesity is an epidemic, a major public health concern, and is a significant risk factor for progression and mortality from prostate cancer. Research from our group and others suggest that weight loss interventions consisting of exercise and reduction in dietary fat may play an important role in the prevention of prostate cancer progression (secondary prevention). For example, our group demonstrated that a diet and exercise weight loss intervention in obese

men reduced the serum IGF-1 and increased serum IGFBP-1, factors known to affect prostate cancer progression in experimental systems. We have also developed unique ex-vivo bioassays that indicated that sera from obese men that underwent a weight loss intervention had anti-mitogenic and pro-apoptotic effects on prostate cancer cells *in vitro*, and this was a result of the above mentioned changes in IGF axis parameters. In addition, our group demonstrated that feeding mice a low-fat diet resulted in decreased prostate tumor growth, increased tumor apoptosis, decreased tumor proliferation (Ki67 staining), and decreased serum and tumor IGF-1 protein levels. Although these studies suggest a weight loss intervention may potentially impact on human prostate cancer progression, studies directly evaluating the effect of weight loss on prostate cancer histology in humans have yet to be performed. Furthermore, intermediate serum biomarkers to monitor the success of weight loss interventions on prostate cancer progression have not been established. To this end, we are now proposing a prospective randomized trial to evaluate if diet and exercise-induced weight loss in overweight and obese men for 4-9 weeks prior to radical prostatectomy results in decreased proliferation and increased apoptosis in prostate cancer tissue. We also propose to study whether weight loss prior to radical prostatectomy impacts on the expression of IGF-axis-related proteins in prostate cancer tissue and on the circulating levels of IGF-1 and IGFBP-1 in patient sera. Our ultimate goals are to determine if weight loss can potentially affect prostate cancer progression through affecting proliferation and apoptosis of prostate cancer tissue in humans, and to establish serum biomarkers for future large-scale secondary prevention trials in overweight and obese prostate cancer survivors to monitor the success of weight loss interventions.

Data presented herein outlines the strong evidence linking obesity and prostate cancer progression. The effect of obesity, weight loss, and exercise on the hormonal milieu including the IGF axis proteins, and the potential impact on prostate cancer progression is outlined in the background section of the research protocol.

Obesity and Prostate Cancer Progression: Prior studies examining the relationship between adult body mass index (BMI) and risk of developing prostate cancer have been mixed with several large studies showing a positive association¹⁻³ and others showing no association.^{4, 5} Of the studies that found a significant association between increased BMI and risk of developing prostate cancer, several found that the risk for developing advanced disease was even stronger than the risk of developing prostate cancer in general.^{1, 3} Visceral obesity may play an important role in the link between obesity and development of prostate cancer. One study among men in China found that men in the highest quartile of waist-to-hip ratio had an almost 3-fold increased risk for developing prostate cancer.⁶

While the relationship between obesity and prostate cancer risk is unclear, the relationship between obesity and progression and mortality from prostate cancer is well established.^{1, 7-9} Two recent studies, one of which was from our group, utilized large multi-institutional multi-racial databases to address whether increased BMI was associated with higher biochemical failure rates following radical prostatectomy.^{10, 11} Both studies concluded that obese men were more likely to have higher grade disease, and obesity was an independent predictor of prostate cancer recurrence following radical prostatectomy. Interestingly, both studies found that black men were more likely to be obese, which may explain, in part, the higher mortality from prostate cancer among black men.¹² In regards to obesity and prostate cancer mortality, two large prospective studies deserve particular attention. In 1959 and again in 1982, the American Cancer Society enrolled a cohort of patients for longitudinal studies on cancer, known as the Cancer Prevention Study (CPS) I and II, respectively. Men were then followed for 13 years in CPS-I and 14 years in CPS-II. Together these studies followed a total of 816,268 men during which time there were 5,212 prostate cancer deaths. Both CPS-I and CPS-II reported that

obese men (BMI >30 kg/m²) were significantly more likely to die from prostate cancer with a 27% increased risk of prostate cancer death from CPS-I and a 21% increased risk of death from CPS-II.⁸ More details regarding CPS-II were recently published which showed that severely obese men (BMI >35 kg/m²) were at even greater risk of dying from prostate cancer with a 34% higher risk of prostate cancer death relative to normal weight men.⁹ The data linking obesity with prostate cancer progression and mortality supports the urgent need for further studies evaluating weight loss interventions and prostate cancer progression.

Hormones, Obesity and Prostate Cancer Progression

Sex Hormones and Leptin: Studies on obesity and prostate cancer are complicated by the fact that obesity is not only associated with excess body fat, but also altered serum levels of numerous hormones including testosterone, estrogen, insulin, insulin-like growth factor-I (IGF-I), and leptin, all of which have to some degree been linked to prostate cancer. Whereas androgens,^{13, 14} estrogens,¹⁵ leptin,^{16, 17} and adipokines¹⁸ such as adiponectin may play an important role in prostate cancer progression in obese men, these hormones and growth factors will not be discussed here as the focus of our proposal and our preliminary data points towards the IGF axis proteins.

Insulin: Obesity is associated with insulin resistance and non-insulin dependent diabetes mellitus.¹⁹ It has been hypothesized that insulin resistance may be related to prostate cancer development.²⁰ For example, Hsing et al. found that insulin resistance, diabetes, and elevated insulin/glucose levels increased prostate cancer risk.^{21, 22} Other studies, however found no association or decreased prostate cancer risk in men with diabetes.^{23, 24} Given the amount of conflicting data in the literature it is difficult to determine the true impact of insulin resistance and or diabetes on prostate cancer development or progression.

IGF-I and IGF Binding Proteins: IGF-I is a peptide growth factor and a potent mitogen for the growth of androgen responsive and androgen independent human prostate cancer cell lines.²⁵ IGF-1 plays a pivotal role in regulating cell proliferation, differentiation, and apoptosis.²⁶ Epidemiological investigations have found a positive correlation between elevated serum IGF-I levels and the risk of developing prostate cancer.²⁷⁻²⁹ Tissue levels of IGF-1 appear to be a critically important factor during initiation and progression of prostate cancer.^{26, 30} Animal studies have demonstrated that caloric restriction decreases growth of prostate tumors and decreases serum IGF-1 levels.^{31, 32} The activity of IGF-1 is modulated by high-affinity IGF-binding proteins (IGFBP's 1-6).³³ Circulating levels of IGFBPs-1 and -2 vary in response to nutritional status and in response to changes in energy metabolism.²⁶ This is particularly true for IGFBP-1, which is perhaps the most dramatically regulated serum protein in response to diet, with levels changing up to fifty-fold in response to fasting.³⁴ In the energy-restricted state, which is strongly protective against many forms of tumors including prostate cancer, circulating levels of IGFBP-1 are increased, and to a lesser degree IGFBP -2 are also increased.^{30, 35, 36} Overeating and obesity, on the other hand, lead to hyperinsulinemia and decreased levels of IGFBP-1, although the effect of insulin on serum IGFBP-2 levels in humans is less clear.^{26, 37, 38} Serum IGFBP-1 levels have also been shown to increase following low-fat diet and exercise interventions, probably due, in part, to changes in serum insulin.³⁸

Dietary Fat and Prostate Cancer Progression: The mechanisms through which dietary fat may impact on prostate cancer progression (and conversely decreasing dietary fat may prevent prostate cancer progression) are multiple and include increased energy intake, inflammatory pathways, alteration of sex steroid hormones, and effects on serum and tissue growth factors.^{31, 41-43} Epidemiological studies have demonstrated a significant positive association between

dietary fat intake and the risk of developing advanced prostate cancer.^{45, 46} For example, Fradet et al. prospectively monitored dietary fat intake, prostate cancer progression and survival in 384 men diagnosed with prostate cancer between 1990 and 1992. They found that increased consumption of saturated fat was associated with an increased risk of dying from prostate cancer.⁴⁷ Other epidemiologic studies have failed to observe a correlation between dietary fat intake and overall risk of prostate cancer, but importantly, no studies have shown an increased risk of prostate cancer with a low-fat diet.^{48, 49}

Exercise and Prostate Cancer: In a recent review of the literature on physical activity and the risk for prostate cancer, Thune and Furberg found that 14 of 28 epidemiological studies reported that increased occupational or leisure-time activity reduced the risk for prostate cancer by 10-70 percent.⁵⁰ Only four studies reported the opposite relationship. The majority of epidemiologic data supports the association between more intensive exercise and lower prostate cancer risk.⁵⁰ Barnard et al. recently examined serum from men that attended the Adult Fitness Program at the University of Nevada Las Vegas for at least 10 years and compared prostate cancer relevant biomarkers with an age matched group of overweight men with a sedentary lifestyle.⁵¹ Results of prostate cancer biomarkers were more favorable in the exercise group including decreased serum IGF-I levels, increased serum IGFBP-1 levels, and decreased serum-stimulated growth of a human prostate cancer cell line (LNCaP) in vitro when cultured in media containing patient sera.⁵¹ There is a great need for further studies examining the effects of exercise on serum and tissue biomarkers in prostate cancer patients.

Preclinical Studies in Energy Restriction and Prostate Cancer: Several recent preclinical studies support the role of caloric restriction for preventing the development and progression of prostate cancer. Mukherjee et al. utilized two transplantable prostate tumor models: (1) androgen-dependent Dunning R3327-H adenocarcinoma in rats and (2) androgen-sensitive LNCaP human carcinoma in severe combined immunodeficient mice. They found that caloric restriction reduced tumor growth in both models relative to animals fed ad libitum, and increased apoptosis was found in tumors from the energy restricted groups relative to the ad libitum groups.⁵¹ Boileau et al. induced prostate tumors in rats by subjecting them to N-methyl-N-nitrosourea and testosterone (a well established model for prostate cancer), and found a reduced proportion of mice developed prostate tumors in the caloric restriction group relative to an ad libitum fed group.⁵² Likewise, Suttie et al. found decreased development of prostate cancer in TRAMP mice that were restricted in calories (relative to an ad libitum group), and tumors from the restricted group had reduced tumor grade.⁵³ In summary, pre-clinical models of energy restriction strongly support the conduct of a prospective randomized trial in men evaluating weight loss and biologically relevant tumor markers.

[figure not shown]
Significance: If we find that the proposed weight loss intervention increases apoptosis and/or decreases proliferation in malignant epithelium, this will form the basis for immediate initiation of larger scale trials evaluating weight loss for prostate cancer survivors. In our experience, the most likely design for this type of larger trial in the future would be to enroll men with a progressively rising PSA following primary therapy for prostate cancer with the aim of evaluating if weight loss can decrease the PSA doubling time over 1-year. Emerging data from our group and others suggests that PSA doubling time directly relates to mortality in men with prostate cancer and therefore represents an important surrogate for future large scale trials.^{54,55} Our research team has direct experience with this large scale experimental design as we are presently conducting a multicenter prospective randomized trial of this nature testing a botanical dietary supplement juice from pomegranates. In the event that the proposed weight loss trial demonstrates an effect, we have extensive collaborative relationships in place to make feasible

a larger scale definitive trial in the future evaluating weight loss in men with rising PSA levels as described above.

Relevance to Veteran's Health: The proposed research is directly relevant to Veteran's health. Given that the majority of the VA population is aging males, prostate cancer remains a significant health concern for our patients. Prostate cancer is second to skin malignancies in incidence of prostate cancer in the United States and is the second leading cause of male cancer deaths.⁵⁶ Obesity is also a major health concern among Veterans. Research from our group found approximately 70% of veterans with prostate cancer that underwent radical Prostatectomy were overweight or obese. Given the sometimes long and protracted course of prostate cancer, if weight loss is ultimately found to decrease prostate cancer progression, this will be an important non-toxic intervention for patients to consider that have elected watchful waiting, or as an adjuvant to other primary therapies.

